14 APPENDIX-3: LIST OF ANY BLEEDING

Procedure for definition of “any bleeding”

Step 1. To extract the following group A or group B from MDV data base.

Group A: ICD-10 name includes [REDACTED] (bleeding)" or [REDACTED] (ecchymoma)"

Group B: Disease name includes [REDACTED] (bleeding)" or [REDACTED] (ecchymoma)"

Step 2. To select disease names considered to be relevant to side effect of OAC individually from disease names excluded in Step 1.

Step 3. To exclude disease names which are not considered to be relevant to side effect of OAC from the disease names included in Step 1.

ICD-10	ICD10Name
A162	Tuberculosis of lung, without mention of bacteriological or histological confirmation
A165	Tuberculous pleurisy, without mention of bacteriological or histological confirmation
B303	Acute epidemic haemorrhagic conjunctivitis (enteroviral)
D500	Iron deficiency anaemia secondary to blood loss (chronic)
D62	Acute posthaemorrhagic anaemia
D66	Hereditary factor VIII deficiency
D683	Haemorrhagic disorder due to circulating anticoagulants
D698	Other specified haemorrhagic conditions
D699	Haemorrhagic condition, unspecified
E078	Other specified disorders of thyroid
E274	Other and unspecified adrenocortical insufficiency
G361	Acute and subacute haemorrhagic leukoencephalitis [Hurst]
G951	Vascular myopathies
G968	Other specified disorders of central nervous system
H052	Exophthalmic conditions
H113	Conjunctival haemorrhage
H168	Other keratitis
H208	Other iridocyclitis
H210	Hyphaema
H313	Choroidal haemorrhage and rupture
H350	Background retinopathy and retinal vascular changes
H356	Retinal haemorrhage
H357	Separation of retinal layers
H405	Glaucoma secondary to other eye disorders
H431	Vitreous haemorrhage

ICD-10	ICD10Name
H448	Other disorders of globe
H470	Disorders of optic nerve, not elsewhere classified
H603	Other infective otitis externa
H669	Otitis media, unspecified
H738	Other specified disorders of tympanic membrane
H922	Otorrhagia
I213	Acute transmural myocardial infarction of unspecified site
I230	Haemopericardium as current complication following acute myocardial infarction
I312	Haemopericardium, not elsewhere classified
I600	Subarachnoid haemorrhage from carotid siphon and bifurcation
I601	Subarachnoid haemorrhage from middle cerebral artery
I602	Subarachnoid haemorrhage from anterior communicating artery
I603	Subarachnoid haemorrhage from posterior communicating artery
I604	Subarachnoid haemorrhage from basilar artery
I605	Subarachnoid haemorrhage from vertebral artery
I606	Subarachnoid haemorrhage from other intracranial arteries
I607	Subarachnoid haemorrhage from intracranial artery, unspecified
I608	Other subarachnoid haemorrhage
I609	Subarachnoid haemorrhage, unspecified
I610	Intracerebral haemorrhage in hemisphere, subcortical
I611	Intracerebral haemorrhage in hemisphere, cortical
I613	Intracerebral haemorrhage in brain stem
I614	Intracerebral haemorrhage in cerebellum
I615	Intracerebral haemorrhage, intraventricular
I616	Intracerebral haemorrhage, multiple localized
I618	Other intracerebral haemorrhage
I619	Intracerebral haemorrhage, unspecified
I620	Subdural haemorrhage (acute)(nontraumatic)
I621	Nontraumatic extradural haemorrhage
I629	Intracranial haemorrhage (nontraumatic), unspecified
I638	Other cerebral infarction
I690	Sequelae of subarachnoid haemorrhage
I691	Sequelae of intracerebral haemorrhage
I780	Hereditary haemorrhagic telangiectasia
I788	Other diseases of capillaries
I841	Internal hemorrhoid with other complications
I844	External hemorrhoid with other complications
I848	Unspecified hemorrhoid with other complications
I850	Oesophageal varices with bleeding
I864	Gastric varices
J041	Acute tracheitis

ICD-10	ICD10Name
J339	Nasal polyp, unspecified
J90	Pleural effusion, not elsewhere classified
J942	Haemothorax
J950	Tracheostomy malfunction
K049	Other and unspecified diseases of pulp and periapical tissues
K068	Other specified disorders of gingiva and edentulous alveolar ridge
K121	Other forms of stomatitis
K137	Other and unspecified lesions of oral mucosa
K148	Other diseases of tongue
K226	Gastro-oesophageal laceration-haemorrhage syndrome
K228	Other specified diseases of oesophagus
K250	Acute with haemorrhage
K252	Gastric ulcer, Acute with both haemorrhage and perforation
K254	Gastric ulcer, Chronic or unspecified with haemorrhage
K256	Gastric ulcer, Chronic or unspecified with both haemorrhage and perforation
K260	Duodenal ulcer, Acute with haemorrhage
K262	Duodenal ulcer, Acute with both haemorrhage and perforation
K264	Duodenal ulcer, Chronic or unspecified with haemorrhage
K266	Duodenal ulcer, Chronic or unspecified with both haemorrhage and perforation
K270	Acute duodenal tumor with haemorrhage
K284	Gastrojejunal ulcer, Chronic or unspecified with haemorrhage
K290	Acute haemorrhagic gastritis
K571	Diverticular disease of small intestine without perforation or abscess
K573	Diverticular disease of large intestine without perforation or abscess
K625	Haemorrhage of anus and rectum
K661	Haemoperitoneum
K762	Central haemorrhagic necrosis of liver
K768	Other specified diseases of liver
K85	Acute pancreatitis
K920	Haematemesis
K921	Melaena
K922	Gastrointestinal haemorrhage, unspecified
L508	Other urticaria
M250	Haemarthrosis
N029	Recurrent and persistent haematuria, Unspecified
N288	Other specified disorders of kidney and ureter
N300	Acute cystitis
N304	Irradiation cystitis
N309	Cystitis, unspecified
N328	Other specified disorders of bladder

ICD-10	ICD10Name
N368	Other specified disorders of urethra
N421	Congestion and haemorrhage of prostate
N488	Other specified disorders of penis
N501	Vascular disorders of male genital organs
N645	Other signs and symptoms in breast
N830	Follicular cyst of ovary
N831	Corpus luteum cyst
N836	Haematosalpinx
N837	Haematoma of broad ligament
N838	Other noninflammatory disorders of ovary, fallopian tube and broad ligament
N898	Other specified noninflammatory disorders of vagina
N908	Other specified noninflammatory disorders of vulva and perineum
N921	Excessive and frequent menstruation with irregular cycle
N922	Excessive menstruation at puberty
N923	Ovulation bleeding
N924	Excessive bleeding in the premenopausal period
N930	Postcoital and contact bleeding
N938	Other specified abnormal uterine and vaginal bleeding
N939	Abnormal uterine and vaginal bleeding, unspecified
N950	Postmenopausal bleeding
O208	Other haemorrhage in early pregnancy
O209	Haemorrhage in early pregnancy, unspecified
O441	Placenta praevia with haemorrhage
O469	Antepartum haemorrhage, unspecified
O679	Intrapartum haemorrhage, unspecified
O695	Labour and delivery complicated by vascular lesion of cord
O717	Obstetric haematoma of pelvis
O720	Third-stage haemorrhage
O721	Other immediate postpartum haemorrhage
O722	Delayed and secondary postpartum haemorrhage
O901	Disruption of perineal obstetric wound
O902	Haematoma of obstetric wound
P021	Fetus and newborn affected by other forms of placental separation and haemorrhage
P100	Subdural haemorrhage due to birth injury
P101	Cerebral haemorrhage due to birth injury
P102	Intraventricular haemorrhage due to birth injury
P103	Subarachnoid haemorrhage due to birth injury
P109	Unspecified intracranial laceration and haemorrhage due to birth injury
P120	Cephalhaematoma due to birth injury
P269	Unspecified pulmonary haemorrhage originating in the perinatal period

ICD-10	ICD10Name
P510	Massive umbilical haemorrhage of newborn
P519	Umbilical haemorrhage of newborn, unspecified
P523	Unspecified intraventricular (nontraumatic) haemorrhage of fetus and newborn
P524	Intracerebral (nontraumatic) haemorrhage of fetus and newborn
P528	Other intracranial (nontraumatic) haemorrhages of fetus and newborn
P529	Intracranial (nontraumatic) haemorrhage of fetus and newborn, unspecified
P540	Neonatal haematemesis
P542	Neonatal rectal haemorrhage
P543	Other neonatal gastrointestinal haemorrhage
P544	Neonatal adrenal haemorrhage
P545	Neonatal cutaneous haemorrhage
P546	Neonatal vaginal haemorrhage
P549	Neonatal haemorrhage, unspecified
P580	Neonatal jaundice due to bruising
P581	Neonatal jaundice due to bleeding
R040	Epistaxis
R041	Haemorrhage from throat
R042	Haemoptysis
R048	Haemorrhage from other sites in respiratory passages
R049	Haemorrhage from respiratory passages, unspecified
R18	Ascites
R195	Other faecal abnormalities
R233	Spontaneous ecchymoses
R31	Unspecified haematuria
R571	Hypovolaemic shock
R58	Haemorrhage, not elsewhere classified
S000	Superficial injury of scalp
S001	Contusion of eyelid and periocular area
S002	Other superficial injuries of eyelid and periocular area
S003	Superficial injury of nose
S004	Superficial injury of ear
S005	Superficial injury of lip and oral cavity
S007	Multiple superficial injuries of head
S008	Superficial injury of other parts of head
S013	Open wound of ear
S019	Open wound of head, part unspecified
S050	Injury of conjunctiva and corneal abrasion without mention of foreign body
S051	Contusion of eyeball and orbital tissues
S063	Focal brain injury

ICD-10	ICD10Name
S064	Epidural haemorrhage
S065	Traumatic subdural haemorrhage
S066	Traumatic subarachnoid haemorrhage
S068	Other intracranial injuries
S098	Other specified injuries of head
S100	Contusion of throat
S101	Other and unspecified superficial injuries of throat
S141	Other and unspecified injuries of cervical spinal cord
S241	Other and unspecified injuries of thoracic spinal cord
S271	Traumatic haemothorax
S272	Traumatic haemopneumothorax
S278	Injury of other specified intrathoracic organs
S279	Injury of unspecified intrathoracic organ
S301	Contusion of abdominal wall
S302	Contusion of external genital organs
S341	Other injury of lumbar spinal cord
S361	Injury of liver or gallbladder
S368	Injury of other intra-abdominal organs
S369	Injury of unspecified intra-abdominal organ
S370	Injury of kidney
S378	Injury of other pelvic organs
S390	Injury of muscle and tendon of abdomen, lower back and pelvis
S400	Contusion of shoulder and upper arm
S408	Other superficial injuries of shoulder and upper arm
S500	Contusion of elbow
S501	Contusion of other and unspecified parts of forearm
S600	Contusion of finger(s) without damage to nail
S601	Contusion of finger(s) with damage to nail
S701	Contusion of thigh
S800	Contusion of knee
S801	Contusion of other and unspecified parts of lower leg
S901	Contusion of toe(s) without damage to nail
S902	Contusion of toe(s) with damage to nail
T009	Multiple superficial injuries, unspecified
T060	Injuries of brain and cranial nerves with injuries of nerves and spinal cord at neck level
T090	Superficial injury of trunk, level unspecified
T093	Injury of spinal cord, level unspecified
T140	Superficial injury of unspecified body region
T144	Injury of nerve(s) of unspecified body region
T145	Injury of blood vessel(s) of unspecified body region
T146	Injury of muscles and tendons of unspecified body region

ICD-10	ICD10Name
T794	Traumatic shock
T810	Haemorrhage and haematoma complicating a procedure, not elsewhere classified
T811	Shock during or resulting from a procedure, not elsewhere classified
T876	Other and unspecified complications of amputation stump
T905	Sequelae of intracranial injury
	Subgaleal hemorrhage
	Intracranial hemorrhage

ICD-10, International Statistical Classification of Diseases and Related Health Problems

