Any intracranial hemorrhage event after index date	Outcome (secondary endpoint)	Intracranial hemorrhage after index date will be identified using hospital claims which had an intracranial hemorrhage diagnosis code as the first listed ICD-10 or disease code (Appendix-2). Time to any intracranial hemorrhage will be defined as the number of days from the index date to the occurrence of the first intracranial hemorrhage event.

^{1,2} Any bleeding will be defined based on definitions listed in Appendix-3. Among any bleeding events, bleeding events that requires hospitalization will be defined as “major bleeding”.

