16 APPENDIX-5: SAFETY ENDPOINTS

Disease	ICD10 code	Standard disease code	Note
Intracranial bleeding	I600		Subarachnoid haemorrhage from carotid siphon and bifurcation
	I601		Subarachnoid haemorrhage from middle cerebral artery
	I602		Subarachnoid haemorrhage from anterior communicating artery
	I603		Subarachnoid haemorrhage from posterior communicating artery
	I604		Subarachnoid haemorrhage from basilar artery
	I605		Subarachnoid haemorrhage from vertebral artery
	I606		Subarachnoid haemorrhage from other intracranial arteries
	I607		Subarachnoid haemorrhage from intracranial artery, unspecified
	I608		Other subarachnoid haemorrhage
	I609		Subarachnoid haemorrhage, unspecified
	I610		Intracerebral haemorrhage in hemisphere, subcortical
	I611		Intracerebral haemorrhage in hemisphere, cortical
	I613		Intracerebral haemorrhage in brain stem
	I614		Intracerebral haemorrhage in cerebellum
	I615		Intracerebral haemorrhage, intraventricular
	I616		Intracerebral haemorrhage, multiple localized
	I618		Other intracerebral haemorrhage
	I619		Intracerebral haemorrhage, unspecified
	I620		Subdural haemorrhage (acute)(nontraumatic)
	I621		Nontraumatic extradural haemorrhage
	I629		Intracranial haemorrhage (nontraumatic), unspecified
	I690		Sequelae of subarachnoid haemorrhage
	I691		Sequelae of intracerebral haemorrhage
	S064		Epidural haemorrhage
	S065		Traumatic subdural haemorrhage
	S066		Traumatic subarachnoid haemorrhage
	S068		Other intracranial injuries
GI bleeding	I850		Oesophageal varices with bleeding
	K226		Gastro-oesophageal laceration-haemorrhage syndrome
	K228		Other specified diseases of oesophagus
	K250		Acute with haemorrhage
	K252		Gastric ulcer, Acute with both haemorrhage and perforation
	K254		Gastric ulcer, Chronic or unspecified with haemorrhage
	K256		Gastric ulcer, Chronic or unspecified with both haemorrhage and perforation
	K260		Duodenal ulcer, Acute with haemorrhage
	K262		Duodenal ulcer, Acute with both haemorrhage and perforation
	K264		Duodenal ulcer, Chronic or unspecified with haemorrhage
	K266		Duodenal ulcer, Chronic or unspecified with both haemorrhage and perforation
	K270		Acute duodenal tumor with haemorrhage
	K284		Gastrojejunal ulcer, Chronic or unspecified with haemorrhage

K290	Acute haemorrhagic gastritis
K625	Haemorrhage of anus and rectum
K920	Haematemesis
K921	Melaena
K922	Gastrointestinal haemorrhage, unspecified

CCI

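### The SAP's GI-bleeding code list leaves out intestinal diverticular and gastric-variceal codes that its any-bleeding list counts as bleeding, so such bleeds can be major bleeds without being GI bleeds

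*SAP*

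**What the plan says.** Protocol Section 6 and SAP Section 4.2 name major GI bleeding and any GI bleeding among the secondary objectives, without restricting them to a part of the gut.

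SAP Section 8.2 sets the parent endpoints in its footnote: "Any bleeding will be defined based on definitions listed in Appendix-3". It continues: "Among any bleeding events, bleeding events that requires hospitalization will be defined as" major bleeding.

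SAP Appendix-3 was built from disease names. Step 1 extracts entries whose ICD-10 name or disease name contains a bleeding or ecchymoma term. Step 2 adds others: "To select disease names considered to be relevant to side effect of OAC individually from disease names excluded in Step 1". Step 3 removes some: "To exclude disease names which are not considered to be relevant to side effect of OAC". The resulting table includes:

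- K571, "Diverticular disease of small intestine without perforation or abscess"
- K573, "Diverticular disease of large intestine without perforation or abscess"
- I864, "Gastric varices"

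SAP Appendix-5 has a separate GI-bleeding list. It contains none of these three codes, but it does contain K228, "Other specified diseases of oesophagus". No visible sentence explains the difference between the two lists.

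For the GI endpoints, Section 8.2 requires a GI-bleeding code as the first listed code. Major GI bleeding also requires the DPC category for the disease behind the hospitalisation (category 21). The section cites a Table 8 in the appendix for major GI bleeding and an unnumbered appendix for any GI bleeding.

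**The concern.** The SAP accepts these three codes as bleeding when it counts any and major bleeding, then drops them when it counts bleeding in the gut, although all three are gastrointestinal by name. An admission recorded under K573 would be a primary major-bleeding event while the same patient stays event-free in both GI analyses. If the bleed ends treatment with the index OAC, the patient is then censored at discontinuation (Protocol Section 7.2, SAP Section 10.1.3), so a GI bleed becomes a censored record.

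At stake is the classification of events in a named secondary objective. SAP Section 10.1.8 plans Cox models for 2 GI endpoints × 4 NOAC-warfarin comparisons × 2 methods (PS matching and IPTW) = 16 hazard ratios, all using this list. A reader comparing major bleeding with major GI bleeding would wrongly place these bleeds outside the gut.

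**Working it through.** The plan states no figure on this point to reproduce. The check compares the two code lists.

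**Inputs**

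- Appendix-5 GI list, 18 codes: I850, K226, K228, K250, K252, K254, K256, K260, K262, K264, K266, K270, K284, K290, K625, K920, K921, K922.
- The digestive-tract and related codes of Appendix-3.

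**Step 1: is the GI list a subset of Appendix-3?** Yes. All 18 codes are in Appendix-3.

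**Step 2: which Appendix-3 codes are left out of the GI list?**

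| Group | Codes |
|---|---|
| Gastrointestinal by name | K571, K573, I864 |
| Haemorrhoids with other complications | I841, I844, I848 |
| Less clearly luminal, or other sites (not part of this point) | K661, R195, R18, K762, K768, K85, and the oral codes K049, K068, K121, K137, K148 |

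**Step 3: does a visible rule explain the gap?**

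- *Only labels that state bleeding.* This fits 17 of the 18 codes. K228 breaks the rule. Appendix-3 also selects on disease names, while its table prints ICD labels, so a label silent on bleeding does not show that the retained disease name is silent.
- *Upper gut only.* K625 (anus and rectum) and K922 (unspecified site) are in the list.
- *Varices left out on purpose.* I850, bleeding oesophageal varices, is in the list.

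**Step 4: could redaction explain it?** The visible GI list is in code order. I864 would fall between I850 and K226, and K571 and K573 between K290 and K625. Both places are visible. A redacted block follows K922.

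**Step 5: how does one event run through the definitions?** Take a hospitalisation whose category-21, first-listed diagnosis is a retained disease name under K573.

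| Endpoint | Role in Section 8.2 | Counts? |
|---|---|---|
| Major bleeding | Primary | Yes |
| Any bleeding | Secondary | Yes |
| Major GI bleeding | Secondary | No, unless a listed GI code also qualifies |
| Any GI bleeding | Secondary | No, unless a listed GI code also qualifies |

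**Step 6: size of the list change.** Adding entries under the three codes would extend the GI list from 18 to 18 + 3 = 21 ICD categories. With the three haemorrhoid codes it would be 21 + 3 = 24. No code frequencies are given, so this cannot be converted into events or interval widths.

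**The case against.** The strongest reply is that Appendix-3 is a deliberately broad list and the GI list a deliberately specific one. Appendix-3 also carries lung tuberculosis, hereditary factor VIII deficiency, acute pancreatitis, ascites and many newborn codes, so membership is weak evidence that a printed code means bleeding. With 17 of 18 GI labels naming a bleed, K228 might be the stray entry, and explaining or removing it would also make the list consistent. Part of this stands: the printed ICD labels cannot settle what was intended, and whole codes must not be carried across, because that would admit diverticular disease or varices without bleeding. It does not remove the inconsistency, because Section 8.2 makes Appendix-3 the operative definition of bleeding and no rule for the narrower list is stated.

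Two uncertainties also stand. Appendix-5 is only inferred to be the operative list, since the table and appendix that Section 8.2 cites for GI bleeding cannot be found in the visible text. And the redacted block cannot be excluded entirely: Appendix-5 has a column for standard disease codes, and in Appendix-4 such codes follow the ICD codes. The table of contents shows a redacted entry after Appendix-5, which suggests a separate section instead.

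A reader might infer more than the documents support:

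- *The components fail to add up to the parent endpoint.* No text requires additivity. Each endpoint counts its own first event, and Appendix-3 covers eye, urinary and skin sites that have no component endpoint.
- *The GI hazard ratios are distorted.* That needs drugs to differ by bleeding site within the gut, on which the documents are silent.
- *Every such bleed is lost.* Some patients may also have a qualifying listed code such as K921 or K922.

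**Conclusion.** The point holds as an unexplained inconsistency between the SAP's own lists. Bleeds under K571, K573 and I864 count as any bleeding and, when hospitalised, as major bleeding. They do not count as GI bleeding unless another listed GI code qualifies. I841, I844 and I848 are in the same position and need the same disease-name review.

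The effect is confined to the two GI secondary endpoints. The definitions of major bleeding and stroke/SE are untouched. How many events are misclassified, and whether any GI hazard ratio would rise or fall, cannot be derived from the documents. The conclusion assumes that Appendix-5 is the operative GI list and that the redacted text does not supply the missing entries. This is a minor point, worth making because it is cheap to correct before programming.

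**What to change.** Before programming:

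1. Add to the GI list the bleeding-specific disease names that Appendix-3 retained under K571, K573 and I864. Do not add the whole ICD codes.
2. Apply the same disease-name rule to I841, I844 and I848.
3. Print the retained disease names or standard disease codes in the SAP. Appendix-3 shows only ICD labels, so the restriction cannot be programmed from the document as it stands.
4. Correct the GI cross-references in Section 8.2 so that they point to Appendix-5.

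If the omission was intended, the SAP should state the reason and say how K228 fits it.

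The cost is a small amount of code-list work. The GI endpoint may also become slightly less comparable with earlier studies, if those used the list as it now stands.

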15 APPENDIX-4: EFFECTIVENESS ENDPOINTS

Disease	ICD10 code	Standard disease code	Note
Hemorrhage stroke	I60		
	I61		
	I62		Exclude non-traumatic extradural haemorrhage
Ischemic stroke	I63		
		3489032	
		4371003	
		4379014	
		3448002	
		3448028	
		3489029	
		3489035	
		4379006	
TIA	I63		
		H340	
		G450	
		G451	
		G458	
		G459	
Systemic embolism	I740		Include only abdominal aortic embolism
	I741		Include only aortic embolism
	I742		Include only acute arterial occlusive disease of arteries of upper extremities
	I743		Include only femoral arterial occlusion and acute arterial occlusive disease of arteries of lower extremities
	I744		
	I745		Include only iliac artery embolism
	I748		Include only hepatic artery embolism
	I749		Include only thromboembolism, embolic infarction, aortic embolism
	I748		Include only subclavian artery stenosis

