7.1 FULL ANALYSIS SET

All eligible patients for the study will be included in the analysis.

Inclusion criteria

Patients must meet all of the following criteria to be eligible for the study:

- 1. Diagnosed with AF anytime in the baseline period or on the index date, also have definitive diagnosis of AF anytime in the baseline period, on the index date, or post-index period.*
- 2. Prescribed one of the index OACs (apixaban, edoxaban, or warfarin) on or after the day of AF diagnosis. The first observed prescription will be used to identify the patient's index date and treatment cohort*
- 3. No use of the any OACs during the baseline period (the 180 days before the index date)*
- 4. Age of 18 years or older on the index date.*

Exclusion criteria

Patients meeting any of the following criteria will not be included in the study:

- 1. Having a diagnosis of valvular atrial fibrillation, post-operative atrial fibrillation, rheumatic atrial fibrillation or mechanical-valvular atrial fibrillation during the baseline and post-index period*
- 2. Having a cardiac surgery procedure record during the baseline period*

3. *Having a joint replacement procedure record during the baseline period*
4. *Having a procedure of prosthetic heart valve during the baseline period*
5. *Having a diagnosis of venous thromboembolism during the baseline period*
6. *Female patients with pregnancy during the follow-up period*
7. *Patients prescribed “off-label” doses of OACs (per Japanese package insert of each OAC) or patients treated with OAC but in “off-label” or “contraindicated” manners.*

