8 ENDPOINTS AND COVARIATES

8.1 EFFICACY/ EFFECTIVENESS ENDPOINT(S)

Variable	Role	Operational definition
Stroke/SE (composite) event after index date	Outcome (primary endpoint)	Operational definition of Stroke and SE will follow the operational definition of Stroke event after index date and SE event after index date. Time to events will be defined as the number of days from the index date to the occurrence of the first stroke or SE.
Ischemic stroke event after index date	Outcome (secondary endpoint)	Ischemic stroke after index date not including the index date will be identified using hospital claims which had an ischemic stroke diagnosis code as the first listed ICD-10 diagnosis code (Appendix, Table 5). An event occurrence of ischemic stroke is defined as a case that "01: Disease name which input the most medical resources", "02:Sub-disease name", "11: Main disease name", "21: Disease name behind hospitalization", or "31: Disease name which input the second most medical resources" in DPC database. Time to ischemic stroke will be defined as the number of days from the index date to the occurrence of the first ischemic stroke.
Hemorrhagic stroke event after index date	Outcome (secondary endpoint)	Hemorrhagic stroke after index date not including the index date will be identified using hospital claims which had a hemorrhagic stroke diagnosis code as the first listed ICD-10 diagnosis code (Appendix, Table 5). An event occurrence of hemorrhagic stroke is defined as a case that "01: Disease name which input the most medical resources", "02:Sub-disease name", "11: Main disease name", "21: Disease name behind hospitalization", or "31: Disease name which input the second most medical resources" in DPC database. Time to hemorrhagic stroke will be defined as the number of days from the index date to the occurrence of the first hemorrhagic stroke.
SE event after index date	Outcome (secondary endpoint)	SE after index date not including the index date will be identified using hospital claims which had a SE diagnosis code as the first listed ICD-10 diagnosis code (Appendix, Table 5). An event occurrence of SE is defined as a case that "01: Disease name which input the most medical resources", "02:Sub-disease name",

Variable	Role	Operational definition

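### Appendix-4 counts subclavian artery stenosis as systemic embolism, against Appendix-1, and two sequelae codes can count as new bleeding

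*SAP*

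**What the plan says.** **Systemic embolism.** SAP 8.1 makes the stroke/SE composite the primary effectiveness endpoint and builds it from the separate stroke and SE definitions. Appendix-4 holds the effectiveness codes. Its systemic embolism block carries I748 once with the note "Include only hepatic artery embolism" and again, as its last row, with "Include only subclavian artery stenosis". Appendix-1 also codes systemic embolism, but there I748 is limited to the hepatic entry. The subclavian entry closes the peripheral vascular disorder block.

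**Sequelae.** Appendix-3 (any bleeding) lists I690, I691 ("Sequelae of intracerebral haemorrhage") and T905 ("Sequelae of intracranial injury"). Appendix-5 repeats I690 ("Sequelae of subarachnoid haemorrhage") and I691 under intracranial bleeding. The baseline period in SAP 7.1 is "the 180 days before the index date", and no exclusion criterion there names prior stroke or prior bleeding.

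**Diagnosis position.** For ischemic stroke, SAP 8.1 identifies events from "hospital claims which had an ischemic stroke diagnosis code as the first listed ICD-10 diagnosis code". The next sentence begins "An event occurrence of ischemic stroke is defined as a case that" and names five DPC fields (01, 02, 11, 21, 31). The hemorrhagic stroke and SE cells follow the same pattern. Protocol Table 1 asks for at least one stroke or SE diagnosis in follow-up and sets no position.

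**Major intracranial hemorrhage.** In SAP 8.2 the major bleeding and major GI bleeding cells require field 21. The major intracranial hemorrhage cell does not. Both intracranial cells point to Appendix-2, which lists procedure codes.

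**The concern.** In a claims study without adjudication (Protocol 7.9), the code list and the position rule are the endpoint. A stenosis is not an embolism, and a sequela is not a new bleed. Endpoints are times to first event and follow-up stops at the target outcome, so a sequela coded first also takes the place of any later true bleed.

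If such entries arise independently of treatment, they pull the hazard ratio toward 1. If a history of stroke or bleeding differs between warfarin and NOAC starters beyond what the 180-day baseline captures, the direction is unknown.

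The stenosis row touches a primary endpoint. The sequelae rows touch any bleeding, which is one of the three hypotheses in SAP 6.1, and intracranial hemorrhage, which is secondary.

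**Working it through.** No figure in the plan depends on these rows, so the check is a comparison of lists and definitions.

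**1. Systemic embolism rows**
- Appendix-4: I740, I741, I742, I743, I744, I745, I748 (hepatic), I749, I748 (subclavian) = 9 rows.
- Appendix-1: the same codes with I748 once (hepatic) = 8 rows.
- Difference: 9 − 8 = 1 row, the stenosis. It is also the last row of Appendix-1's peripheral vascular block, so it looks like a leftover from copying. That is an inference.

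**2. Sequelae rows**
- Appendix-5, intracranial: I600–I609 (10) + I610, I611, I613–I616, I618, I619 (8) + I620, I621, I629 (3) + I690, I691 (2) + S064, S065, S066, S068 (4) = 27 rows, of which 2 are sequelae. Their note column gives only the title, with no inclusion or exclusion rule.
- Appendix-3: I690, I691 and T905 = 3 rows.

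**3. Where the sequelae can be counted under SAP 8.2**
- Any bleeding: yes, if first-listed on a hospital claim (all three codes).
- Intracranial hemorrhage: yes, on the same condition (I690 and I691).
- Major bleeding: only if the code also sits in field 21.
- Stroke/SE composite: no. Appendix-4 lists I60–I63 and specific disease codes for stroke, not I69.

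**4. Stroke/SE position.** Read together, the two conditions in SAP 8.1 require a first-listed code that also sits in one of the five fields. Read with the second sentence governing, any of the five fields suffices, including the sub-disease field and the second-most-resource field. The second reading can only admit the same events or more. The SAP does not say which applies.

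**5. Major intracranial hemorrhage.** The SAP 8.2 footnote defines major bleeding as any-bleeding events that require hospitalization. Its markers sit on the major-bleeding and any-bleeding rows. All 27 intracranial codes of Appendix-5 also appear in Appendix-3, so intracranial hemorrhage is a subset of any bleeding and the footnote covers it by content. The cell does not repeat the condition, and the codes are in Appendix-5, not Appendix-2.

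**The case against.** **Appendix-3 was filtered by disease name.** Its three steps add and remove individual disease names according to relevance to an OAC side effect, and the table prints parent ICD-10 titles. Rows such as lung tuberculosis, pleural effusion or ascites make sense only as headings for selected names, so a title need not show what was kept. This stands for T905, whose title names an injury and not a bleed. It does not rescue I690 and I691: their titles themselves denote late effects of haemorrhage, the selection steps left them in, and Appendix-5 repeats them without restriction.

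**Prior events are adjusted for.** Baseline bleeding and baseline stroke or SE are propensity-score covariates (SAP 10.1.1). That reduces imbalance in recorded history. It does not stop a sequela from being counted as an outcome.

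**Three rival stroke/SE rules.** A reader might infer that Protocol Table 1 is a third competing definition and that the primary endpoint is left to the programmer. The documents do not support that. Protocol 7.7 leaves detail to the SAP and lets it modify the plan, so Table 1 can be read as a summary that SAP 8.1 makes operational, and SAP 8.1 does name the qualifying fields. What remains is how its two conditions combine.

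**Major and any intracranial hemorrhage returning the same events.** The two cells, read alone, invite this inference. The footnote supplies the hospitalization condition by content, and the visible tables in SAP 10.1.8 contain no row for any intracranial hemorrhage.

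**Conclusion.** The point holds and should be fixed before analysis. Two parts are wrong as written: the stenosis row in Appendix-4, which contradicts Appendix-1 and enters the primary composite, and I690 and I691 in Appendix-3 and Appendix-5. The position rule is a lesser clarification. The major intracranial hemorrhage cell and its pointer are drafting corrections.

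The size is not derivable. The documents give no event counts by code or by diagnosis field, and 1 of 9, 2 of 27 and 3 rows say nothing about how often the codes occur. A reader might assume a share of miscoded events and compute a diluted hazard ratio or a loss of power, but no such share has a source in the documents.

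With the cohorts held fixed, deleting the rows can only leave the number of patients with a counted event unchanged or reduce it. The effect of settling the position rule depends on the rule chosen.

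**What to change.** - **Appendix-4:** delete the subclavian stenosis I748 row so that the list matches Appendix-1.
- **Appendices 3 and 5:** delete I690 and I691 from the endpoint lists. For T905, keep only disease names that denote a new bleed and print them. The SAP gives no separate code list for the baseline bleeding covariate. If Appendix-3 also serves there, say whether these codes stay in for history.
- **SAP 8.1:** state before analysis one rule for how the first-listed condition and the five fields combine, and run the other as a sensitivity analysis. Align Protocol Table 1, by amendment if the change is major under Protocol 7.7.
- **SAP 8.2:** repeat the field-21 condition in the major intracranial hemorrhage cell, and point both intracranial cells to Appendix-5.

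The cost is edits to SAP 8.1, 8.2 and Appendices 3 to 5, matching changes in the endpoint code, one extra stroke/SE run for each of the four comparisons, and possibly a protocol amendment. No new data are required. The downside is that removing the rows may lower event counts by an unknown amount.
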